5.1 Inclusion Criteria

All enrolled patients must meet all of the following inclusion criteria:

- Subject is 18 years or older;
- Subject is willing and able to provide written informed consent;
- Diagnosis of migraine, based on a history of at least 5 attacks per month with the following primary headache characteristics:
 - Headache attacks lasting 4-72 hours (untreated or unsuccessfully treated);
 - Headache has at least two of the following characteristics:
 - unilateral location;
 - pulsating quality;
 - moderate or severe pain intensity;
 - aggravation by or causing avoidance of routine physical activity (*e.g.* walking or climbing stairs);
 - Headache occurs with at least one of the following symptoms:
 - nausea and/or vomiting;
 - photophobia and phonophobia;
- Subject has experienced at least 4 migraine attacks in the last month, with at least two migraine attacks resulting in severe pain prior to the use of any abortive medications;
- Migraines are not attributed to another disorder.

5.2 Exclusion Criteria

All enrolled patients must meet none of the following exclusion criteria:

- Subjects participating in another prospective, interventional clinical study;
- Subjects with other light sensitive conditions, such as iritis;
- Subjects who have less than 4 headache days per month with the above characteristics;
- Chronic migraine subjects (defined as subjects who experience a minimum of 15 headache days per month);
- Subjects with headaches due to medication overuse (defined as regular use of headache medication for a minimum of 10 days per month, for a minimum period of 3 months);
- Subjects who have had any change in their migraine treatment within 4 weeks prior to study enrollment.
- Subjects whose family members are currently participating in this study, or are employees of the study site, Avulux, or the coordinating CRO.

6. Study Procedures

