6.4 Procedures and Assessments

Subjects will be directed to:

- apply the study glasses at the first onset of aura, or as soon as possible once they experience symptoms consistent with the onset of a migraine attack.
- avoid taking abortive medication for the first four hours of a migraine attack. If abortive medications cannot be avoided, the subject should document use.
- record the following information for the first (and all subsequent) severe or very severe migraine headaches that they experience while enrolled in the study:
 - The date and time of symptom onset;

¹ Kwong WJ and Pathak DS. Validation of the eleven-point pain scale in the measurement of migraine headache pain. *Cephalgia* 2007; 27: 336-342.

- The pain score (as assessed on the 11-point pain scale) just prior to the application of the study glasses (score needs to be greater than or equal to 6 to qualify as a severe or very severe headache);
- The time at which the study glasses are applied;
- Whether the subject was wearing prescription eyewear in addition to the study glasses, or whether the study glasses alone were worn;
- The pain score (as assessed on the eleven-point pain scale) 2 hours after the study glasses are applied;
- The pain score (as assessed on the eleven-point pain scale) 4 hours after the study glasses are applied;
- The type of abortive medication taken (if any) to control headache symptoms, the dosage taken, and the time at which the medication is taken; and
- Any experience of light sensitivity within 4 hours after the study glasses are applied, and the time at which light sensitivity is first experienced.

Subjects will participate in the study for a maximum of four (4) weeks \pm 3 days after enrollment; if a given subject does not experience a severe or very severe migraine headache within four (4) weeks, that subject will not be included in the evaluable study population.

Study coordinators will contact subjects once per week to ensure they are wearing the study device as instructed, and that they are recording the requested information related to their headaches. These weekly contacts will also enable coordinators to identify and address any barriers to adherence with the protocol.

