11.1 Sample Size Justification

A pilot evaluation of the Avulux® and control/sham devices (n = 10 subjects using each type of device) demonstrated that users of the Avulux® device reported a mean decrease of 4.1 points in pain score (standard deviation = 1.9 points) after an elapsed time of 2 hours, and users of the placebo device reported a mean decrease of 1.9 points in pain score (standard deviation = 1.5 points) after an elapsed time of 2 hours. The difference between the performance of the two devices was statistically significant ($p = 0.004$).

Assuming that subjects with severe or very severe migraine headaches achieve a mean 4-point improvement in pain score when using the investigative device and at most a mean 2-point improvement when using the control/sham device, and assuming a standard deviation of at

most 2.0 points when estimating the mean difference in pain scores in individual study subjects after application of either device, a sample size of 27 subjects per study arm provides a minimum statistical power of 95% to detect a significant difference in mean results for the primary endpoint variable between the two (2) device types, at a significance level of $\alpha = 0.05$. Given an estimated dropout rate of up to 20% in each study arm, a minimum of 34 subjects per arm (or 68 total subjects) are required to be enrolled in this study.

The above assumptions imply that the mean improvement in pain score after 2 hours will be at least 2 points higher for the Avulux® device than for the control/sham device. Meta-analyses have shown that the minimal clinically important difference (MCID) to detect changes in acute pain as measured on the 11-point pain scale is 1.7 points;^{2,3} therefore, a 2-point difference in mean improvement between study devices is considered to be clinically meaningful.

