11.2 Proposed Analyses

A statistical analysis plan, containing detailed information regarding the proposed statistical analyses of study data, will be created and approved prior to database lock.

Unless otherwise stated, all statistical testing will be two-sided and will be performed using a significance level of $\alpha = 0.05$.

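### Earlier wearers of the study lenses are not excluded, and the diary does not record tint or non-prescription filtering eyewear

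*Combined protocol and SAP*

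**What the plan says.** Section 5.2 opens its list with "All enrolled patients must meet none of the following exclusion criteria" and gives seven items. Two come near the point. One bars people who are currently in another interventional study. The other bars a change of migraine treatment in the four weeks before enrolment. None mentions earlier use of either study lens, the pilot, or other light-filtering glasses. The inclusion criteria in 5.1 are silent on this, and 6.2 collects migraine history without naming lens use.

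Section 11.1 shows that earlier wearers exist: the pilot had "n = 10 subjects using each type of device". Section 6.2 says that subjects are blinded to device type. Section 2 describes an active lens containing a dye, and a sham that blocks almost nothing at the same wavelengths.

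For eyewear during an attack, the section 6.4 diary has one item: "Whether the subject was wearing prescription eyewear in addition to the study glasses, or whether the study glasses alone were worn". Subjects are not told to avoid other tinted lenses. Coordinators check weekly that the device is worn as instructed.

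At the end of the study subjects are asked which device they think they had (section 6.4), and section 11.2.8 analyses the answers with two published blinding indices.

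**The concern.** The primary endpoint is the subject's own 0–10 score, so it depends on the blind. A person who has worn one of these lenses before may recognise it, or recognise that the new pair is different. Recognition acts after allocation, so randomisation does not balance it out. A subject who believes the lens is active may expect relief, and one who believes it is sham may not, which would widen the difference between arms.

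The second gap acts the other way. Photophobia is among the diagnostic features in 5.1, and light sensitivity is an exploratory endpoint in 4.3. A sham subject who reaches for tinted lenses during an attack may obtain some of the filtering that the trial is meant to test, which would narrow the difference.

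The plan treats medication more carefully. Abortive medication is recorded by type, amount and time, and section 11.2.5 compares its early use between arms. Filtering eyewear would act through the device's own proposed mechanism, yet it has no comparable record, and section 11 does not use even the existing eyewear item.

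**Working it through.** **Step 1: do existing items close the gaps?**

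- *Concurrent study (5.2).* It covers present participation only, so a former pilot participant passes.
- *Treatment change within four weeks (5.2).* Older or stable lens use passes, and the item does not say that eyewear counts as treatment.
- *Eyewear item (6.4).* It has two answers: prescription eyewear as well, or study glasses alone. Tinted prescription lenses are captured as eyewear but not as tinted. Sunglasses, and study glasses taken off in favour of another pair, have no answer.
- *End-of-study guess (6.4, 11.2.8).* It can show that subjects knew their arm. Earlier use is not collected, so it cannot show why.

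**Step 2: reproduce the planned sample size.** The inputs are in section 11.1: subjects "achieve a mean 4-point improvement in pain score when using the investigative device and at most a mean 2-point improvement" on sham, so the difference is 4 − 2 = 2 points; SD at most 2.0; 27 evaluable per arm; 95% power; α = 0.05. Section 11.2 adds that "all statistical testing will be two-sided".

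Standard error = SD × √(2/n) = 2.0 × √(2/27) = 0.544. Noncentrality = 2/0.544 = 3.67 on 2 × 27 − 2 = 52 degrees of freedom. Noncentral-t power is 95.0% at 27 per arm and 94.2% at 26, so 27 reproduces. With 20% dropout, 27/0.80 = 33.75, which rounds up to 34 per arm and 68 in total. These figures are not in dispute.

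**Step 3: sensitivity to filtering obtained by sham subjects.** The documents give no rate, so the share f is assumed. In the extreme case each such subject gains the full 2 points, and the difference becomes 2 × (1 − f). The last column also lets the mixture widen the sham variance to 4 + 4f(1 − f), averaged with the active arm's 4.

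| f (assumed) | Difference | Difference / 0.544 | Power, SD 2.0 | Power, wider sham SD |
|---|---|---|---|---|
| 0 | 2.0 | 3.67 | 95.0% | 95.0% |
| 5% | 1.9 | 3.49 | 92.9% | 92.3% |
| 10% | 1.8 | 3.31 | 90.1% | 88.8% |
| 20% | 1.6 | 2.94 | 82.2% | 79.3% |
| 30% | 1.4 | 2.57 | 71.4% | 67.1% |

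A partial effect costs less. If 20% of sham subjects gained half the effect, the difference would be 2 − 0.20 × 1 = 1.8, as in the 10% row at SD 2.0 (90.1%).

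**Step 4: sensitivity to recognition of the arm.** Suppose there is no true effect, a share g recognises the arm, and expectation moves the active-minus-sham difference among them by b points (both assumed). The spurious difference is g × b. Two-sided rejection at 27 per arm and SD 2.0 is then:

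- g = 10%, b = 1: difference 0.1, rejection 5.4%
- g = 10%, b = 2: difference 0.2, rejection 6.5%
- g = 20%, b = 2: difference 0.4, rejection 11.1%

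Steps 3 and 4 move the result in opposite directions, and neither f, g nor b is in the documents.

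**The case against.** The case for leaving the plan alone has several parts.

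- *Blinding is assessed.* A reader might infer that unblinding would go unseen. The documents do not support that: the guess in 6.4 and the indices in 11.2.8 may reveal it. What stands is narrower. The question comes at the end, 11.2.8 limits it to subjects who complete all procedures, and it cannot be linked to earlier exposure.
- *Eyewear is recorded.* A reader might infer that the diary ignores other eyewear. It does not; it captures additional prescription eyewear. The gap is tint and non-prescription lenses.
- *Departures from instructed use are addressed.* Weekly contacts check wear, and 11.2.1 removes non-compliant subjects from the per-protocol set. However, that set serves only the exploratory endpoints, and a deviation that is neither defined nor recorded cannot be removed reliably.
- *Exposure is hypothetical.* Section 11.1 does not say whether the two groups of 10 were different people, whether they knew their device, or whether they come from this trial's sites. Nothing shows how many candidates use filtering glasses. This stands in full and limits the claim to a possibility of unknown size.
- *The full-effect case is extreme.* Section 2 describes a dye targeted at specified wavelengths, so nothing supports treating ordinary sunglasses as equivalent. This also stands.
- *Recording does not prevent use.* This is correct: the diary change would not restore power lost to sunglasses.

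**Conclusion.** The point holds as an inexpensive improvement, with medium confidence. Two facts are firm: earlier wearers of either study lens are eligible, and tinted or non-prescription filtering eyewear worn during an attack cannot be identified from the planned data. The size of the consequence is not known.

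Two stronger conclusions might be drawn, and neither is supported. The first is that the trial is biased in favour of the device, or against it. The two mechanisms oppose each other and neither has a documented frequency, so the net bias cannot be signed. The second is that the fix buys back the difference between 95% and 90%, 82% or 71% power. Those figures rest on an assumed 10%, 20% or 30% of sham subjects obtaining the full effect elsewhere. They show how sensitive the comparison is in an extreme case, not what the change would gain.

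The reason to act is that the blind protects a self-reported endpoint in a 68-subject trial, and eyewear that goes unrecorded at the time of an attack cannot be reliably recovered later.

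**What to change.** - **Section 5.2:** add an exclusion for previous use of the Avulux or sham lenses, including in the pilot evaluation.
- **Section 6.2:** ask at baseline about use of any other light-filtering migraine glasses. Recording this is enough; excluding such users would narrow the population for a less certain gain.
- **Section 6.4:** extend the eyewear item to record any tinted, photochromic or sunglass lens worn between application of the study glasses and the 4-hour score, with type and time.
- **Section 11.2.5, or the detailed analysis plan promised in 11.2:** tabulate that item by arm next to the primary result.

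The cost is a few candidates lost at screening, one baseline question, one longer diary item and one table. The planned 27 evaluable and 34 enrolled per arm, and the primary test, stay as they are.

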6.1 Consent Procedures

After Institutional Review Board/Ethics Committee (IRB/EC) approval for the study is obtained at a given clinical site, the investigator (or appropriate designee) at the site will identify

potential subjects for the study, based on the inclusion/exclusion criteria outlined in Section 4. Eligible subjects will be asked to provide written informed consent. The informed consent process will be documented for each subject and will include a thorough discussion of study procedures involved. Each subject participating in the study shall sign and date the consent form prior to the initiation of any study procedures.

6.2 Enrollment and Randomization of Study Subjects

Subjects will be asked to provide demographic information (date of birth, gender, race/ethnicity) and relevant medical history related to migraine headaches. Subjects who meet all inclusion criteria and none of the exclusion criteria, and who provide written informed consent, will be enrolled in the study. Enrolled subjects will then be randomized to the Avulux® study glasses vs. control/sham study arm, with allocation on a 1:1 basis; subjects will be provided with the device specific to their assigned study arm. Subjects will be blinded to the type of device being assessed (both the blocking abilities when worn).

6.3 Pain Scale

Subjects will be asked to rate their headache pain using an 11-point scale, *i.e.* on an integer scale from 0 to 10 inclusive, with 0 indicating no pain and 10 indicating the worst pain imaginable. The scale can be interpreted clinically as follows:

- 10: worst pain imaginable;
- 8-9: very severe pain;
- 6-7: severe pain;
- 4-5: moderate pain;
- 1-3: mild pain;
- 0: no pain.

The 11-point pain scale has been validated for use in migraine headache evaluations.¹

6.4 Procedures and Assessments

Subjects will be directed to:

- apply the study glasses at the first onset of aura, or as soon as possible once they experience symptoms consistent with the onset of a migraine attack.
- avoid taking abortive medication for the first four hours of a migraine attack. If abortive medications cannot be avoided, the subject should document use.
- record the following information for the first (and all subsequent) severe or very severe migraine headaches that they experience while enrolled in the study:
 - The date and time of symptom onset;

¹ Kwong WJ and Pathak DS. Validation of the eleven-point pain scale in the measurement of migraine headache pain. *Cephalgia* 2007; 27: 336-342.

- The pain score (as assessed on the 11-point pain scale) just prior to the application of the study glasses (score needs to be greater than or equal to 6 to qualify as a severe or very severe headache);
- The time at which the study glasses are applied;
- Whether the subject was wearing prescription eyewear in addition to the study glasses, or whether the study glasses alone were worn;
- The pain score (as assessed on the eleven-point pain scale) 2 hours after the study glasses are applied;
- The pain score (as assessed on the eleven-point pain scale) 4 hours after the study glasses are applied;
- The type of abortive medication taken (if any) to control headache symptoms, the dosage taken, and the time at which the medication is taken; and
- Any experience of light sensitivity within 4 hours after the study glasses are applied, and the time at which light sensitivity is first experienced.

Subjects will participate in the study for a maximum of four (4) weeks \pm 3 days after enrollment; if a given subject does not experience a severe or very severe migraine headache within four (4) weeks, that subject will not be included in the evaluable study population.

Study coordinators will contact subjects once per week to ensure they are wearing the study device as instructed, and that they are recording the requested information related to their headaches. These weekly contacts will also enable coordinators to identify and address any barriers to adherence with the protocol.

After completion of study activities, subjects will return the glasses specific to their study arm, and be asked to complete a study questionnaire, to provide feedback regarding the wearability and ease of use of the glasses. Subjects will also be asked to provide an opinion as to which type of device they believe they were assigned to (Avulux[®] vs. control/sham vs. do not know).

7. Safety Reporting

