7.1 Adverse Events

An adverse event (AE) is defined as an undesirable physical, psychological, or behavioral effect experienced by a subject related to headaches in conjunction with his/her participation in the clinical study, whether or not device related. Any subject may experience adverse events or complications while enrolled in the study. Should they occur, these events will be reported to the sponsor as detailed in section 7.3.1.

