7.3 Reporting of Events

7.3.1 Adverse Events

Adverse events will be reported to the sponsor in a timely manner. A case report form shall be completed for each event, with description of the event, onset date, end date, relation to study device, any treatment rendered and the outcome.

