8.2 Benefits

The anticipated benefit of the device is the reduction in headache severity in patients with migraine headaches. Information gained from this study may aid in the future management of patients with episodic migraine headaches.

9. Subject Withdrawal

In accordance with Good Clinical Practice (GCP) guidelines, subjects who have consented to participate in the study are free to withdraw consent and discontinue participation in the study at any time, and without prejudice to further treatment as required for their condition.

If a subject decides to discontinue participation in the study, the investigator will note the reason for the discontinuation (and any potential AEs) on the applicable case report form.

10. Administrative Considerations

This protocol was designed and will be conducted, recorded, and reported in compliance with Good Clinical Practice (GCP) guidelines and with applicable U.S. Food and Drug Administration (FDA) Investigational Device Exemption (IDE) regulations.

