11.2.9 Adverse Event Data

Analyses of adverse event data shall be conducted with respect to all enrolled subjects who participated in the use of either the active device or the control/sham device during study procedures.

For each study device, the number of adverse events (AEs) shall be tabulated, and descriptive statistics shall be utilized to summarize the severity of AEs and their relationship to study procedures for each device.

All serious adverse events (SAEs) will be listed individually.

⁵ James KE, Bloch DA, Lee KK *et al.* An index for assessing blindness in a multi-centre clinical trial: disulfiram for alcohol cessation – a VA cooperative study. *Stat Med* 1996, 15: 1421-1434.

⁶ Bang H, Ni L and Davis CE. Assessment of blinding in clinical trials. *Control Clin Trials* 2004, 25: 143-156.

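### No systematic adverse event enquiry is described for subjects who stay in the study, and only event counts are planned, so adverse events are likely to be under-captured and subject-level incidence goes unreported

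*Combined protocol and SAP*

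**What the plan says.** Section 6.4 sets out what subjects record and when staff speak to them. The diary covers symptom onset, pain scores, time of application, eyewear, abortive medication and light sensitivity. On the weekly calls it says "Study coordinators will contact subjects once per week to ensure they are wearing the study device as instructed", and the calls also check that the diary is being kept. It adds: "These weekly contacts will also enable coordinators to identify and address any barriers to adherence with the protocol". At the end, subjects return the glasses, complete a questionnaire "to provide feedback regarding the wearability and ease of use of the glasses", and guess their allocation.

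Section 7.1 defines an AE as "an undesirable physical, psychological, or behavioral effect experienced by a subject related to headaches" and says: "Should they occur, these events will be reported to the sponsor as detailed in section 7.3.1". Section 7.3.1 says: "A case report form shall be completed for each event, with description of the event, onset date, end date, relation to study device". Section 9 says that when a subject discontinues "the investigator will note the reason for the discontinuation (and any potential AEs) on the applicable case report form".

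The analysis in 11.2.9 uses all enrolled subjects who used either device. Its summary measure is: "For each study device, the number of adverse events (AEs) shall be tabulated". Severity and relationship are described, and serious events are listed. Section 11.2 promises a separate, more detailed SAP before database lock.

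**The concern.** Sections 7.1 and 7.3.1 say what happens once an event is known. They do not say how it becomes known. For a subject who completes the study, no written step prompts staff to ask. A report of few AEs could then mean that few occurred or that nobody asked.

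The planned summary adds a second problem. Subjects use the glasses at every attack for up to four weeks, and section 5.1 recruits people with at least four attacks in the last month. One person can have the same effect repeatedly. A count of events does not show how many people were affected, which is what a reader needs in order to judge tolerability against the statement in 8.1 that no risks are anticipated.

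**Working it through.** **The plan's own figures.** The documents give no AE rate or AE-based sample size. The only figure needed is the arm size in 11.1: 27/(1 − 0.20) = 33.75, rounded up to 34 per arm. This reproduces. The AE set may be smaller than 34, because it counts only subjects who used a device.

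**Step 1. Contacts set side by side.**
- Diary (6.4): no AE item, apart from light sensitivity as a symptom.
- Weekly contact (6.4): wear, recording, adherence barriers; no AE item.
- Closing questionnaire (6.4): wearability, ease of use, guessed device; no AE item.
- Sections 7.1 and 7.3.1: AEs from any subject are reportable, one form per event; no method or schedule of enquiry.
- Discontinuation (section 9): the investigator notes any potential AEs. This is the only contact with an AE instruction.

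**Step 2. Events against subjects.** Suppose one subject of 34 has the same effect at five attacks. Events per subject are 5/34 = 14.7%, while subjects affected are 1/34 = 2.9%. More generally, assume 12 events in an arm of 34. The count fits anything from 1/34 subjects (2.9%, exact 95% interval 0.1% to 15.3%) to 12/34 (35.3%, interval 19.7% to 53.5%).

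**Step 3. Incomplete capture.** Let p be the true per-subject risk, d the proportion discontinuing, and s the fraction captured without enquiry. Assume full capture at discontinuation. The observed rate is p × [d + (1 − d) × s]. None of p, s or a difference in d comes from the documents; 11.1 allows up to 20% dropout in each arm and gives no imbalance. Take p = 20% in both arms, and d = 20% in one arm and 5% in the other:

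| s | Observed, d = 20% | Observed, d = 5% | Difference (points) | Ratio |
|---|---|---|---|---|
| 0.3 | 8.8% | 6.7% | 2.1 | 1.31 |
| 0.5 | 12.0% | 10.5% | 1.5 | 1.14 |
| 0.8 | 16.8% | 16.2% | 0.6 | 1.04 |
| 1.0 | 20.0% | 20.0% | 0 | 1.00 |

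For the first row: 0.20 × (0.20 + 0.80 × 0.3) = 0.088 and 0.20 × (0.05 + 0.95 × 0.3) = 0.067. The shortfall from 20% is much larger than the gap between arms. If d and s are equal in both arms, the gap is zero.

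**Step 4. What no recorded events would show.** With 0 of 34 affected, the upper end of the exact two-sided 95% interval is 1 − 0.025^(1/34) = 10.3% (one-sided 95% limit: 1 − 0.05^(1/34) = 8.4%). This bounds the recorded rate. If only a fraction s is captured throughout, the bound on the true risk is 10.3%/s: 34.3% at s = 0.3, 20.6% at s = 0.5 and 12.9% at s = 0.8.

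**The case against.** A reader might infer that the plan makes a comparable per-subject AE rate by arm impossible. The documents do not support that. Section 7.3.1 requires a form for each event and 11.2.9 defines the analysis set, so subjects with at least one recorded AE can be counted by device. The later SAP could specify the table.

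A reader might also infer that AEs are actively sought at discontinuation and nowhere else, so that the arms are ascertained differently. Section 9 says that AEs are noted, which is an instruction to record rather than to ask, and section 7 makes AEs reportable for every subject. Procedures are the same in both randomised arms. Uneven capture needs a difference in discontinuation or in volunteering, and even the unfavourable case in Step 3 gives only 2.1 percentage points.

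Some effects may also surface indirectly. Section 8.1 expects any discomfort to be relieved by taking the glasses off, and that could emerge in the wear check or the wearability feedback. Safety is not a study objective or endpoint, and no AE test is planned.

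All of this stands, and it limits the point. It does not close the gap in collection. Discomfort mentioned on a weekly call can be handled as an adherence barrier, with nothing telling the coordinator to log an AE. A SAP can repair the table, but it cannot recover events that nobody asked about.

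**Conclusion.** The plan describes no systematic AE enquiry for subjects who remain in the study and plans no subject-level AE incidence by device. The more certain effect is under-capture in both arms; a between-arm distortion is conditional and probably small. The sizes in Steps 3 and 4 rest on assumed risks, capture fractions and discontinuation rates, and show only direction and scale. The ambiguity of event counts does not depend on those capture assumptions: one subject with repeat events can dominate the count in an arm of about 34. The efficacy analyses are not affected. The change is worth making because it is cheap and because the collection part must be in place while subjects are being followed.

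**What to change.** 1. **Section 6.4.** At each weekly contact and at the final visit, ask every subject in both arms the same open, non-leading question, for example whether they have had any health problem since the last contact. Log the answer, including none.
2. **Section 7.1.** Reconcile the AE definition, now limited to headache-related effects, with that question, so that every elicited event can be classified.
3. **Section 11.2.9.** By device, report the number and percentage of subjects with at least one AE, using the stated AE analysis set as denominator, with an exact two-sided 95% interval. Show event counts alongside.

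The cost is one scripted question at contacts already planned, a short edit to the definition and an extra table column. The downside is more minor events to process. Endpoints and sample size do not change.
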